### **Study Schema**

## 1.0 Objectives

1.1 The primary objectives of the study are to determine:

- a. the ability of intravesical BCG immunotherapy to enhance tumor-specific immunity as measured by autologous T cells proliferation following co-culture with autologous monocyte-derived dendritic cells pulsed with autologous tumor lysate

1.2 Secondary objectives of the study are to determine:

- a. the immune effects of BCG in the tumor microenvironment and tumor-draining lymph nodes
- b. the extent to which BCG is processed and presented by tumors cells and/or antigen-presenting cells
- c. the ability of BCG to elicit tumor necrosis/apoptosis in invasive disease
- d. the pathologic stage of disease following BCG treatment
- e. to determine if immune changes elicited by BCG in patients with bladder cancer will provide an opportunity for benefit from mTOR inhibition in tumor milieu

## 2.0 Background

### 2.1 Overview

Urothelial carcinoma of the bladder (UCB) accounted for 70,530 new cases of cancer and 14,680 cancer-related deaths in the United States during 2010^1. Of these new cases, approximately 25% presented as invasive tumors involving the muscular wall of the bladder. Transurethral resection of bladder tumor (TURBT) is an endoscopic procedure that allows for histopathologic assessment and disease staging. TURBT is the primary diagnostic procedure for new and recurrent bladder tumors. TURBT can also be therapeutic for small or non-muscle invasive tumors. However, when muscle-invasive disease is detected, the standard of care involves bladder removal or radical cystectomy (RC) and urinary diversion.

Despite aggressive surgical treatment with bladder removal, up to 50% of patients undergoing RC will experience disease recurrence. Chemotherapy given both before and after surgery has been investigated to improve survival for these patients. Neoadjuvant chemotherapy renders only a modest improvement in survival- approximately 5-7% absolute benefit in 5-year recurrence free survival. Nevertheless neoadjuvant chemotherapy has not been widely adopted due to concerns of toxicity for a modest benefit. In addition, many consider that giving adjuvant chemotherapy for only those patients with high risk pathologic features is a better alternative than treating all patients with neoadjuvant chemotherapy. Current research efforts, therefore, are aimed towards identifying less toxic regimens for use in the neoadjuvant setting. Such effective therapies, especially using those agents with low to moderate toxicity that are easily administered, would be a significant advance in the treatment of invasive bladder cancer. The development of novel, effective therapies, remains an area of unmet need.

### 2.2 Pre-surgical trial

Pre-surgical drug testing is an excellent venue in which paired tumor tissue can be evaluated before and after exposure to a drug to address target specificity, drug delivery, physiologic effects on tumor growth and apoptosis, and correlation of biomarkers with clinical activity. Pre-surgical trials have been conducted in radical cystectomy populations where patients were given drugs for 4-7 weeks prior to surgery. This approach has been acceptable given the evidence that delaying cystectomy for more than 3 months is not associated with a worse clinical outcome. In our protocol, we will seek to characterize the immune effects of intravesical administration in patients undergoing radical cystectomy to help elucidate the anticancer immune mechanisms of BCG in patients with bladder cancer.

### 2.3 BCG immunotherapy

BCG immunotherapy is the mainstay treatment for high-risk non-muscle invasive bladder cancer. BCG specifically, and Mycobacteria generally, have long been known to be potent immune stimulators but the mechanism of action of BCG in cancer remains incompletely understood. BCG reduces bladder cancer relapse by 50% and without it, the risk for cancer relapse is extremely

high (45-80% in non-muscle invasive disease). In animal models, it has been established that BCG could be effective to treat bladder cancer through immune mechanisms mediating anti-cancer immunity against other cancers, including T cells, NK cells and IFN- $\gamma$ . Nevertheless, many mechanistic details are lacking, notably to what extent BCG generates BCG-specific and tumor-specific immunity and whether BCG affects tumor tolerance. Recently, it was demonstrated that BCG efficacy is mediated, at least in part, through stimulation and recruitment of T cells into peritumoral draining lymph nodes. This finding has important implications for the utilization of BCG as discussed below.

Currently BCG is principally used to manage non-muscle invasive bladder cancer and has not been employed to treat muscle-invasive disease, since muscle-invasive disease requires bladder removal. However, to date, BCG is the most immunostimulant utilized in bladder cancer there is increasing evidence that BCG could improve tumor-specific immunity. If BCG can improve tumor-specific immunity, then it could be used as an adjuvant therapy in the management of bladder cancers of all stages, including muscle-invasive disease. For example, BCG given to patients with muscle-invasive disease prior to cystectomy could improve tumor-specific immunity and enable patients to improve tumor clearance in cases of nodal or distant metastasis. By increasing tumor-specific immunity and memory T cell responses, BCG could also enable sustained long-term protection from recurrent disease.

#### 2.4 Rapamycin and immune modulation.

mTOR is a protein kinase that regulates cell growth, proliferation, and other key elements of cell survival. Rapamycin (sirolimus) has long been used in combination with immunosuppressive agents to prevent organ allograft rejection. However, there is no published human study of normal subjects that shows that rapamycin alone is immune suppressive. In fact, recent publications specifically looking at rapamycin immune effects demonstrate that rapamycin boosts immunity to infections, accelerates memory CD8 $^{+}$  T cell differentiation, and improves antigen-specific immunity. Further, rapamycin fed to mice prolongs lifespan, which is inconsistent with significant immunosuppression. Finally, immune modulating properties of mTOR inhibition include effects on T cells, interferon (IFN)- $\gamma$  and other immune mediators critical to anti-cancer immune defenses. In preclinical studies, we found rapamycin to improve immune responses and improve the activity of BCG. In secondary objectives, we aim to clarify the effect of BCG in the tumor milieu to determine mTOR inhibition could be beneficial. Specifically, we aim to measure the quantity of regulatory immune activity including PD-1 expression and Treg cells which could negatively influence BCG's activity. If these populations are elevated, mTOR inhibition may be beneficial, as we have observed rapamycin to decrease PD-1 T cells.

#### 3.0 Drug Information (TICE® BCG)

3.1 **Description:** TICE® BCG for intravesical use, is an attenuated, live culture preparation of the *Bacillus of Calmette and Guerin* (BCG) strain of *Mycobacterium bovis*. The TICE® strain was developed at the University of Illinois from a strain originated at the Pasteur Institute. The medium in which the BCG organism is grown for preparation of the freeze-dried cake is composed of the following ingredients: glycerin, asparagine, citric acid, potassium phosphate, magnesium sulfate, and iron ammonium citrate. The final preparation prior to freeze drying also contains lactose. The freeze-dried BCG preparation is delivered in glass vials, each containing 1 to 8 x 10^8 colony forming units (CFU) of TICE® BCG which is equivalent to approximately 50 mg wet weight. Determination of in-vitro potency is achieved through colony counts derived from a serial dilution assay. A single dose consists of 1 reconstituted vial (see DOSAGE AND ADMINISTRATION). For intravesical use the entire vial is reconstituted with sterile saline. TICE® BCG is viable upon reconstitution. No preservatives have been added.

3.2 **Mechanism of Action:** TICE® BCG induces a granulomatous reaction at the local site of administration. Intravesical TICE® BCG has been used as a therapy for, and prophylaxis against, recurrent tumors in patients with carcinoma *in situ* (CIS) of the urinary bladder, and to prevent recurrence of Stage TaT1 papillary tumors of the bladder at high risk of recurrence. The precise mechanism of action is unknown but is thought to be related to immune stimulation and subsequent immune-mediated cytotoxicity.

3.3 **Toxicology:** Symptoms of bladder irritability, related to the inflammatory response induced, are reported in approximately 60% of patients receiving TICE® BCG. The symptoms typically begin 4–6 hours after instillation and last 24–72 hours. The irritative side effects are usually seen following the third instillation, and tend to increase in severity after each administration.

## 3.4

Clinical Studies: To evaluate the efficacy of intravesical administration of TICE® BCG in the treatment of carcinoma in situ, patients were identified who had been treated with TICE® BCG under six different Investigational New Drug (IND) applications in which the most important shared aspect was the use of an induction plus maintenance schedule. Patients received TICE® BCG (50 mg; 1 to  $8 \times 10^8$  CFU) intravesically, once weekly for at least 6 weeks and once monthly thereafter for up to 12 months. A longer maintenance was given in some cases. The study population consisted of 153 patients, 132 males, 19 females, and 2 unidentified as to gender. Thirty patients lacking baseline documentation of CIS and four patients lost to follow-up were not evaluable for treatment response. Therefore, 119 patients were available for efficacy evaluation. The mean age was 69 years (range: 38–97 years). There were two categories of clinical response: (1) Complete Histological Response (CR), defined as complete resolution of carcinoma in situ documented by cystoscopy and cytology, with or without biopsy; and (2) Complete Clinical Response Without Cytology (CRNC), defined as an apparent complete disappearance of tumor upon cystoscopy. The results of a 1987 analysis of the evaluable patients are shown in Table I.

TABLE I: THE RESPONSE OF PATIENTS WITH CIS BLADDER CANCER IN SIX IND STUDIES

No. (%) of Patients	Entered	Evaluable	CR	CRNC	Overall Response
153	119 (78%)	54 (46%)	36 (30%)	90 (76%)	

A 1989 update of these data is presented in Table II. The median duration of follow-up was 47 months.

TABLE II: FOLLOW-UP RESPONSE OF PATIENTS WITH CIS BLADDER CANCER IN SIX IND STUDIES

Response	1989 Status of 90 Responders (CR or CRNC)			Percent
	1987/CR n = 54	1987/CRNC n = 36	1987 Response n = 90	
CR	30	15	45	50
CRNC	0	0	0	0
Unrelated Deaths	6	6	12	13
Failure	18	15	33	37

There was no significant difference in response rates between patients with or without prior intravesical chemotherapy. The median duration of response, calculated from the Kaplan-Meier curve as median time to recurrence, is estimated at 4 years or greater. The incidence of cystectomy for 90 patients who achieved a complete response (CR or CRNC) was 11%. The median time to cystectomy in patients who achieved a complete response (CR or CRNC) exceeded 74 months. The efficacy of intravesical TICE® BCG in preventing the recurrence of a TaT1 bladder cancer after complete transurethral resection of all papillary tumors was evaluated in two open-label randomized phase III clinical trials. Initial diagnosis of patients included in the studies was determined by cystoscopic biopsies. One was conducted by the Southwestern Oncology Group (SWOG) in patients at high risk of recurrence. High risk was defined as two occurrences of tumor within 56 weeks, any stage T1 tumor, or three or more tumors presenting simultaneously. The second study was conducted at the Nijmegen University Hospital; Nijmegen, The Netherlands. In this study patients were not selected for high risk of recurrence. In both studies treatment was initiated between 1 and 2 weeks after TUR. In the SWOG trial (study 8795) patients were randomized to TICE® BCG or mitomycin C (MMC). Both drugs were given intravesically weekly for 6 weeks, at 8 and 12 weeks, and then monthly for a total treatment duration of 1 year. Cystoscopy and urinary cytology were performed every 3 months for 2 years. Patients with progressive disease or residual or recurrent disease at or after the 6 month follow-up were removed from the study and were classified as treatment failures.

A total of 469 patients was entered into the study: 237 to the TICE® BCG arm and 232 to the MMC arm. Twenty-two patients were subsequently found to be ineligible, and 66 patients had concurrent CIS, and were analyzed separately. Four patients were lost to follow-up, leaving 191 evaluable patients in the TICE® BCG arm and 186 in the MMC arm. Of the patients, 84% were male and 16% were female. The average age of these patients was 65 years old. The Kaplan-Meier estimates of 2 year disease-free survival are shown in Table III. The difference in disease-free survival time between the two groups was statistically significant by the log rank test ( $p=0.03$ ). The 95% confidence interval of the difference in 2 year disease-free survival was  $12\% \pm 10\%$ . No statistically significant differences between the groups were noted in time to tumor progression, tumor invasion, or overall survival.

**TABLE III: RESULTS OF SWOG STUDY 8795**

	TICE® BCG Arm N = 191	MMC Arm N = 186
Estimated Disease-Free Survival at 2 years	57%	45%
95% Confidence Interval (CI)	(50%, 65%)	(38%, 53%)

In the Nijmegen study, the efficacy of three treatments was compared: TICE substrain BCG, Rijksinstituut voor Volksgezondheid en Milieuhygiëne substrain BCG (BCG-RIVM), and MMC. TICE® BCG and BCG-RIVM were given intravesically weekly for 6 weeks. In contrast to the SWOG study, maintenance BCG was not given. Mitomycin C was given intravesically weekly for 4 weeks and then monthly for a total duration of treatment of 6 months. Cystoscopy and urinary cytology were performed every 3 months until recurrence. A total of 469 patients were enrolled and randomized. Thirty-two patients were not evaluable, 17 were ineligible, 15 were withdrawn before treatment, and 50 had concurrent CIS and were analyzed separately, leaving 387 evaluable patients: 117 in the TICE® BCG arm, 134 in the BCG-RIVM arm, and 136 in the MMC arm. Twenty-eight patients (24%) in the TICE® BCG arm, 32 patients (24%) in the BCG-RIVM arm and 24 patients (18%) in the MMC arm had TaG1 tumors. The median duration of follow-up was 22 months (range 3–54 months). The Kaplan-Meier estimates of 2 year disease-free survival are shown in Table IV. The differences in disease-free survival among the three arms were not statistically significant by the log-rank test (p=0.08).

**TABLE IV: RESULTS OF NIJMEGEN STUDY**

	TICE® BCG Arm N = 117	BCG-RIVM Arm N = 134	MMC Arm N = 136
Estimated Disease-Free Survival at 2 years	53%	62%	64%
95% Confidence Interval (CI)	(44%, 64%)	(53%, 72%)	(55%, 74%)

In both the SWOG 8795 study and the Nijmegen study, acute toxicity was more common, and usually more severe, with TICE® BCG than with MMC (see ADVERSE REACTIONS).

3.5 **Warnings:** BCG LIVE (TICE® BCG) is not a vaccine for the prevention of cancer. BCG Vaccine, U.S.P., not BCG LIVE (TICE® BCG), should be used for the prevention of tuberculosis. For vaccination use, refer to BCG Vaccine, U.S.P. prescribing information. TICE® BCG is an infectious agent. Physicians using this product should be familiar with the literature on the prevention and treatment of BCG-related complications, and should be prepared in such emergencies to contact an infectious disease specialist with experience in treating the infectious complications of intravesical BCG. The treatment of the infectious complications of BCG requires long-term, multiple-drug antibiotic therapy. Special culture media are required for mycobacteria, and physicians administering intravesical BCG or those caring for these patients should have these media readily available.

3.5.1 Instillation of TICE® BCG with an actively bleeding mucosa may promote systemic BCG infection. Treatment should be postponed for at least one week following transurethral resection, biopsy, traumatic catheterization, or gross hematuria.

3.5.2 Deaths have been reported as a result of systemic BCG infection and sepsis. Patients should be monitored for the presence of symptoms and signs of toxicity after each intravesical treatment. Febrile episodes with flu-like symptoms lasting more than 72 hours, fever  $\geq 103^{\circ}\text{F}$ , systemic manifestations increasing in intensity with repeated instillations, or persistent abnormalities of liver function tests suggest systemic BCG infection and may require antituberculous therapy. Local symptoms (prostatitis, epididymitis, orchitis) lasting more than 2–3 days may also suggest active infection.

3.5.3 The use of TICE® BCG may cause tuberculin sensitivity. Since this is a valuable aid in the diagnosis of tuberculosis, it is advisable to determine the tuberculin reactivity by PPD skin testing before treatment.

3.5.4 Intravesical instillations of BCG should be postponed during treatment with antibiotics, since antimicrobial therapy may interfere with the effectiveness of TICE® BCG (see PRECAUTIONS). TICE® BCG should not be used in individuals with concurrent infections. Small bladder capacity has been associated with increased risk of severe local reactions and should be considered in deciding to use TICE® BCG therapy.

3.6 **Management of Serious BCG Complications:** Acute, localized irritative toxicities of TICE® BCG may be accompanied by systemic manifestations, consistent with a “flu-like” syndrome. Systemic adverse

effects of 1–2 days' duration such as malaise, fever, and chills often reflect hypersensitivity reactions. However, **symptoms such as fever of  $\geq 38.5^{\circ}\text{C}$  ( $101.3^{\circ}\text{F}$ ), or acute localized inflammation such as epididymitis, prostatitis, or orchitis persisting longer than 2–3 days suggest active infection, and evaluation for serious infectious complication should be considered.**

3.6.1 In patients who develop persistent fever or experience an acute febrile illness consistent with BCG infection, two or more anti-mycobacterial agents should be administered while diagnostic evaluation, including cultures, is conducted and BCG treatment should be discontinued. Negative cultures do not necessarily rule out infection. Physicians using this product should be familiar with the literature on prevention, diagnosis, and treatment of BCG-related complications and, when appropriate, should consult an infectious disease specialist or other physician with experience in the diagnosis and treatment of mycobacterial infections. TICE® BCG is sensitive to the most commonly used antituberculous agents (isoniazid, rifampin and ethambutol). TICE® BCG is not sensitive to pyrazinamide.

### 3.7 PRECAUTIONS:

3.7.1 TICE® BCG contains live mycobacteria and should be prepared and handled using aseptic technique (see **Preparation of Agent** subsection of DOSAGE AND ADMINISTRATION). BCG infections have been reported in health care workers preparing BCG for administration. Needle stick injuries should be avoided during the handling and mixing of TICE® BCG. Nosocomial infections have been reported in patients receiving parenteral drugs which were prepared in areas in which BCG was prepared.

3.7.2 BCG is capable of dissemination when administered by intravesical route and serious reactions, including fatal infections, have been reported in patients receiving intravesical BCG. Care should be taken not to traumatize the urinary tract or to introduce contaminants into the urinary system. Seven to 14 days should elapse before TICE® BCG is administered following TUR, biopsy, or traumatic catheterization.

3.7.3 TICE® BCG should be administered with caution to persons in groups at high risk for HIV infection

### 3.8 Drug Interactions

3.8.1 Drug combinations containing immunosuppressants and/or bone marrow depressants and/or radiation interfere with the development of the immune response and should not be used in combination with TICE® BCG. Antimicrobial therapy for other infections may interfere with the effectiveness of TICE® BCG. There are no data to suggest that the acute, local urinary tract toxicity common with BCG is due to mycobacterial infection and antituberculosis drugs (e.g., isoniazid) should not be used to prevent or treat the local, irritative toxicities of TICE® BCG.

3.8.2 Carcinogenesis, Mutagenesis, Impairment of Fertility: TICE® BCG has not been evaluated for its carcinogenic, mutagenic potentials or impairment of fertility.

### 3.9 Pregnancy

3.9.1 Teratogenic Effects – Pregnancy Category C: Animal reproduction studies have not been conducted with TICE® BCG. It is also not known whether TICE® BCG can cause fetal harm when administered to a pregnant woman or can affect reproductive capacity. TICE® BCG should not be given to a pregnant woman except when clearly needed. Women should be advised not to become pregnant while on therapy.

3.10 Nursing Mothers: It is not known whether TICE® BCG is excreted in human milk. Because many drugs are excreted in human milk and because of the potential for serious adverse reactions from TICE® BCG in nursing infants, it is advisable to discontinue nursing or to discontinue the drug, taking into account the importance of the drug to the mother.

3.11 Pediatric Use: Safety and effectiveness of TICE® BCG for the treatment of superficial bladder cancer in pediatric patients have not been established.

3.12 Geriatric Use: Of the total number of subjects in clinical studies of TICE® BCG, the average age was 66 years old. No overall difference in safety or effectiveness was observed between older and younger subjects. Other reported clinical experience has not identified differences in response between elderly and younger patients, but greater sensitivity of some older individuals to BCG cannot be ruled out.

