**5.0      Eligibility Criteria**

**Inclusion Criteria:**

- 5.1      Have suspected or known invasive ( $\geq T1$ ) bladder cancer
- 5.2      Not be in an immunosuppressed state (e.g. HIV +, use of chronic steroids ( $> 1$  month))
- 5.3      Be able to give informed consent
- 5.4      Be age 18 or older

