**Exclusion Criteria:**

- 5.1.1      Have non-invasive ( $< T1$ ) bladder cancer
- 5.1.2      Is in an immunosuppressed state (e.g. HIV +, use of chronic steroids ( $> 1$  month))
- 5.1.3      Unable to give informed consent
- 5.1.4       $< 18$  or older

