**6.2      Visit 1**

Routine medical history and demographics and physical exam will be performed during the visit (standard care).

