### 6.3 Neoadjuvant Intravesical BCG Instillation

Prior to undergoing routine radical cystectomy (standard care), participant will receive 3 to 6 weeks of neoadjuvant intravesical BCG instillation weekly as part of the research study procedure. The instillation will be scheduled roughly one week apart pending on the clinic's and participant's schedules, and also participant's reaction to the BCG instillation. BCG Week 1 may occur on the same day as Visit 1.

Intravesical BCG will be given as the intervention measure for treatment of bladder cancer. In brief, following sterile preparation, a Foley catheter is introduced into the bladder thru the urethral meatus. The BCG is instilled through gravity drainage and held in the bladder for approximately 2 hours. Instructions are provided to the patient regarding the proper disposal of the BCG. The duration of BCG treatment is allowed to fluctuate between 3-6 weeks for two reasons: (1) This allows for flexibility in scheduling participants for radical cystectomy as the time from enrollment to cystectomy would vary based on surgeon and patient preferences and on operative room availability. In this manner, the surgery date can be established first and then duration of treatment would be based on amount of time available between enrollment and cystectomy date. In our experience, this "time period" is usually 4-6 weeks; (2) The number of BCG treatments needed to elicit expected immune responses is not known. In fact the current paradigm of 6 weekly treatments has little scientific justification but was based on a rather arbitrary dosing schedule; (3) Allowing for multiple durations of therapy, could provide us with the opportunity to explore differences in immune responses across different dosing duration regimens.

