#### 6.3.1 Research Urine Collection and Handling Pre and Post-BCG Instillation (research only)

We will collect a urine sample pre-BCG treatment. We will also collect urine samples post-BCG instillations, specifically the second void, which typically occur 4-6 hours post Intravesical BCG treatment. Participants will be given the following options for collection of urine sample post intravesical BCG treatments:

- a) Participant may remain in the clinic for urine collection  
-OR-
- b) Participant may leave the clinic with a urine sample collection cup and biohazard bag. Participant will be given specific instruction to collect second void post intravesical BCG therapy, and return the sample to the clinic.

Study team member will work with participant on how post BCG therapy urine will be collected and returned to the team. Post-BCG urine collection will take place at weekly during the 3-6 weeks of intravesical BCG treatments. Urine will be processed by centrifugation and the supernatant will be stored separately from the pellet.

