## 7.0 Study Calendar

Study Component/Procedures	Visit 1	BCG Week 1 (may be same day as Visit 1)	BCG Week 2	BCG Week 3	BCG Week 4 a	BCG Week 5 a	BCG Week 6 a	Cystectomy	Post Cystectomy (~within 90 days post cystectomy)
Informed Consent	R								
Medical History, Demographics, Physical Exam	S								
Assessment of AEs		R	R	R	R	R	R		
Urinary symptoms questionnaires	R	R	R	R	R	R	R		
Blood Collection	R*							R	R
Urine Collection (pre and post treatment urine collected on BCG weeks)	R*	R	R	R	R	R	R		
Tissue collection								R	
Tissue blocks from cystectomy procedure								R	

"R" indicates performed only for research purposes and "S" indicates performed for standard care practice

a- Additional BCG treatments beyond week 3 will be given selectively to participants based on time interval between study enrollment and scheduled cystectomy date

\* Optional blood and urine collection

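### The pregnancy caution in section 3.9.1 has no matching exclusion in section 5 and no pregnancy test in the section 7 calendar before the first BCG instillation

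*Combined protocol and SAP*

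**What the plan says.** All references are to the combined protocol and SAP.

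- **Section 3.9.1** says that BCG "should not be given to a pregnant woman except when clearly needed". It adds that fetal harm is neither established nor ruled out, and that women should be told to avoid pregnancy during treatment.
- **Section 5** has four inclusion and four exclusion items, covering stage, immune state, consent and age. The age criterion is "Be age 18 or older", with no upper limit and no restriction by sex. A typical exclusion is "Is in an immunosuppressed state". Pregnancy is not listed.
- **Section 6.2** (Visit 1): "Routine medical history and demographics and physical exam will be performed during the visit".
- **Section 6.2.1** makes the research blood and urine at Visit 1 optional. It also allows extra blood, as required, for screening of eligibility, without naming any test.
- **Section 6.3** gives BCG "as part of the research study procedure" and states: "BCG Week 1 may occur on the same day as Visit 1".
- **Section 6.3.1** states: "We will collect a urine sample pre-BCG treatment".
- **Section 6.3.2** lets the treating physician hold BCG on clinical grounds.
- **Section 7** has no row for a pregnancy test. It does have a urine row, "Urine Collection (pre and post treatment urine collected on BCG weeks"), in which only the Visit 1 sample is marked optional.

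**The concern.** The caution in 3.9.1 can be applied only to a pregnancy that someone knows of or suspects. Eligibility is open to adult women of any age, and consent and first exposure may fall on the same day. A woman with an early pregnancy that neither she nor the physician has recognised could therefore meet every criterion, complete every scheduled procedure and receive BCG.

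The agent is a live organism. Section 3.7.2 warns that it can disseminate from the bladder and that fatal infections have occurred. Exposure here would also come from the research: section 2.3 says that BCG has not been used for muscle-invasive disease, so the clear-need exception would be hard to invoke for those participants. For T1 disease it is arguable, because the same section describes BCG as the main treatment for high-risk non-muscle-invasive tumours. What is at stake is the safety of a rare participant and her fetus, not the validity of the trial's result.

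**Working it through.** The plan states no figure on this point, so there is none to reproduce. The check is a reading of the sections against each other, followed by a rough estimate of size.

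**Step 1: could any listed provision detect an unrecognised pregnancy before the first dose?**

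| Provision | Known or suspected pregnancy | Unrecognised pregnancy |
|---|---|---|
| 3.9.1 caution | Covered | Not triggered |
| Section 5 criteria | No pregnancy item | No pregnancy item |
| 6.2 history and examination | Likely to bring it out | Can miss an early one |
| 6.2.1 extra screening blood | Could be used | No test named, and no section 5 criterion calls for one |
| 6.3.2 physician may hold BCG | Covered | Not triggered |
| Section 7 calendar | No test | No test |

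No row closes the right-hand column. Because 6.3 allows dosing on the day of Visit 1, there need be no interval in which the pregnancy might become apparent.

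**Step 2: how many participants might this touch?**

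Inputs from the documents:
- participants to be consented: 25 (section 9.1);
- share of women: 19/153 = 12.4% in the carcinoma in situ series and 16% in the SWOG trial (both section 3.4). Neither is a cystectomy cohort.

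Assumptions, not in the documents:
- 2% to 10% of the women are of childbearing potential;
- 1% to 5% of those have an unrecognised pregnancy at entry.

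Women enrolled = 25 × share of women:
- low: 25 × 0.1242 = 3.1
- high: 25 × 0.16 = 4.0

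Women needing a test = women × share of childbearing potential:
- low: 3.105 × 0.02 = 0.062
- high: 4.0 × 0.10 = 0.40

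Expected exposed pregnancies = women needing a test × share with an unrecognised pregnancy:
- low: 0.062 × 0.01 = 0.0006
- high: 0.40 × 0.05 = 0.02

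Chance of at least one = 1 − (1 − product of the three shares)^25:
- low: 1 − (1 − 0.1242 × 0.02 × 0.01)^25 = 0.06%
- high: 1 − (1 − 0.16 × 0.10 × 0.05)^25 = 2.0%

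The calculation treats all 25 consented participants as receiving BCG, and some may not. It remains an illustrative range and not a bound, because two of its three shares are assumed.

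**Step 3: can the gap be closed with what the plan already collects?**

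Yes. The BCG-week urine is a scheduled sample, not an optional one, and it includes a pre-treatment collection. Part of it can be tested in the clinic before instillation.

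**The case against.** The strongest reply is that this will almost certainly never matter. The documented ages point to the low end of the range: a mean of 69 in the carcinoma in situ series (3.4) and an average of 66 across BCG studies (3.12). Section 3 is part of the protocol, so its caution already binds the investigator. Other label cautions also stay in section 3 without a calendar row, such as tuberculin skin testing (3.5.3) and the waiting time after resection (3.7.2).

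Much of this stands. The probability is very low, and section 3 is not silent. But the protocol does turn one label caution into entry criteria, namely the one on immune state. And knowing the caution does not help when the pregnancy itself is unknown. Rarity also lowers the cost: if no woman of childbearing potential enrols, no test is done.

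A second reply is that the consent pages have been removed and the schema figure is not shown, and either could hold a test or an exclusion as well as advice. That is right. The omission from sections 5 and 7 is certain; the absence of any safeguard anywhere is not.

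A reader might infer more than the documents support:
- **That the physician can weigh pregnancy only after a test.** A pregnancy may be known or suspected from the history or examination. The gap concerns unrecognised pregnancy alone.
- **That section 5 conflicts with 3.10 on nursing.** Section 3.10 offers the choice of stopping nursing or stopping the drug, so a nursing woman who stops may take part.
- **That advice on contraception is missing.** Section 3.9.1 contains it, and the consent text cannot be seen.

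**Conclusion.** The point holds as a narrow one. Sections 5 and 7 do not carry the pregnancy caution forward, and the visible protocol has no step that would detect an unrecognised pregnancy before the first research instillation. Most likely no participant is affected: the estimate is 0.0006 to 0.02 exposed pregnancies in the whole study, or a 0.06% to 2.0% chance of at least one. This rests on a sex mix borrowed from other BCG populations and on two assumed percentages. No endpoint, analysis or sample size changes. It is a cheap improvement for the sponsor to consider, not a serious flaw.

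**What to change.** 1. **Section 5:** add pregnancy to the exclusion criteria.
2. **Section 7:** add a row for a urine pregnancy test in women of childbearing potential, with the result known before the first instillation.
3. **Section 6.3.1:** state that the test uses part of the pre-BCG urine already collected and is done in the clinic before the sample goes to the research laboratory, where section 6.2.1 has samples de-identified. Same-day dosing then remains possible. The optional Visit 1 samples should not be relied on.

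New nursing or contraception conditions are not needed to close this gap.

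The cost is a short amendment and one urine test in an expected 0.06 to 0.40 women (on the assumptions above), with no added visit or blood draw. There are three drawbacks. A false positive could delay the first dose. A single test covers only the start of a course of 3 to 6 weekly instillations. And an outright exclusion removes, within the study, the clear-need judgement that 3.9.1 leaves to the physician, which is arguable for T1 disease.
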